12.0 CRITERIA FOR THERAPEUTIC RESPONSE/OUTCOME ASSESSMENT

For the purposes of this study, patients will be evaluated for response every 2 months after completing SBRT (approximately 8 weeks, or every 4 cycles). Modified RECIST for mesothelioma and RECIST 1.1 criteria will be used [22]. CT scan of the chest, abdomen, and pelvis will be used for response assessment. The companion CT from an integrated PET/CT examination is suitable for this requirement. As part of the secondary endpoints, progression-free and overall survival will be recorded. Progression-free survival is defined as the length of time from the start of active treatment (avelumab) until removal from study due to progressive disease (defined by modified RECIST 1.1) or death. Removal from study due to toxicity will be counted as censoring. Overall survival is defined as the length of time from the start of active treatment until d e a t h .

Modified RECIST for Mesothelioma [23, 24]

The modified RECIST criteria for mesothelioma use unidimensional measurements of tumor thickness perpendicular to the chest wall or mediastinum. In our protocol, the irradiated lesion is not required to be intrathoracic. This is measured on CT scan in 2 sites at 3 different levels at least 1cm apart. At reassessment, the thickness must be measured at the same position and level. Exhaustive documentation of non-measurable lesions are not required. The sum of tumor diameters is used to measure response.

Definitions of Overall Response	
Complete Response (CR)	Disappearance of all target lesions who no evidence of tumor elsewhere.

Partial Response (PR)	At least a 30% decrease in the sum of diameters of target lesions, taking as reference the baseline sum diameters.
Stable Disease (SD)	Response neither meeting the criteria of CR, PR or PD
Progressive Disease (PD)	At least a 20% increase in the sum of diameters of tumor measurements over the nadir measurement, or appearance of one or more new lesions.

RECIST 1.1

Evaluation of target lesions	
Complete Response (CR)	Disappearance of all target lesions Any pathological lymph nodes (whether target or non-target) must have reduction in short axis to <10 mm.
Partial Response (PR)	At least a 30% decrease in the sum of diameters of target lesions, taking as reference the baseline sum diameters.
Stable Disease (SD)	Neither sufficient shrinkage to qualify for PR nor sufficient increase to qualify for PD, taking as reference the smallest sum of diameters while on study.
Progressive Disease (PD)	At least a 20% increase in the sum of diameters of target lesions, taking as reference the smallest sum on study (this includes the baseline sum if that is the smallest on study). In addition to the relative increase of 20%, the sum must also demonstrate an absolute increase of at least 5 mm. (Note: the appearance of one or more new lesions is also considered progression).

Evaluation of non-target lesions	
Complete Response (CR)	Disappearance of all non-target lesions and normalization of tumor marker level. All lymph nodes must be non-pathological in size (<10mm short axis).
Non-CR/Non-PD	Neither sufficient shrinkage to qualify for PR nor sufficient increase to qualify for PD, taking as reference the smallest sum of diameters while on study.
Progressive Disease (PD)	Unequivocal progression (see comments below) of existing non-target lesions. (Note: the appearance of one or more new lesions is also considered progression).

Time point response: patients with target (+/- non-target) disease			
Target lesions	Non-target lesions	New lesions	Overall response
CR	CR	No	CR
CR	Non-CR/non-PD	No	PR
CR	Not evaluated	No	PR
PR	Non-PD or not all evaluated	No	PR
SD	Non-PD or not all evaluated	No	SD
Not all evaluated	Non-PD	No	NE

PD	Any	Yes or No	PD
Any	PD	Yes or No	PD
Any	Any	Yes	PD

NE =
inevaluable

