4.3 Intervention

The main objective is to evaluate the safety of a novel combination of avelumab (anti-PD-L1 mAb) and stereotactic body radiation therapy (SBRT) for end-stage malignant pleural and peritoneal mesothelioma (MPM).

The safety endpoint of the trial will be assessed based on grade 3 or higher non-hematologic toxicity.

One cycle of avelumab is defined as two weeks. The treatment will consist of one dose of avelumab every other week (Q2W) as well as a short course of SBRT after the first two doses of avelumab. Patients will receive avelumab 10mg/kg as an IV infusion every 2 weeks. Avelumab will be continued up to 24 months or until disease progression. Patients may continue Avelumab after RECIST-defined radiologic progression of disease if the following criteria are met: absence of clinical symptoms or signs indicating clinically significant disease progression; no decline in performance status; absence of rapid disease progression or threat to vital organs or critical anatomical sites [e.g., CNS metastasis, respiratory failure due to tumor compression, spinal cord compression]

requiring urgent alternative medical intervention; no significant, unacceptable or irreversible toxicities related to study treatment.

Patients will be treated with SBRT according to standard image-guided radiation treatment procedures. Patients will have a CT simulation (including 4DCT scanning if clinically indicated) with 2mm slice thickness and daily cone-beam CT verification of patient setup and tumor position. Patients will be treated in ≤ 8 fractions.

To further enhance our current understanding of tumor immunology as well as prognostic biomarkers, we will collect peripheral serum samples before, during and after treatment, and tumor biopsies.

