4.4 Estimated Duration of Subject Participation

Subjects may be treated with avelumab for up to 24 months. All subjects will be followed for survival and assessed every 2 months as per Section 10 for up to 1 year following completion of avelumab or disease progression unless the Principal Investigator or Pfizer elects to end the study.

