9.0 TREATMENT/INTERVENTION PLAN

9.1 Dosing Instructions and Schedule

9.1.1 Avelumab Dosing Instructions and Schedule

One cycle of avelumab is defined as two weeks. Administration of avelumab will commence after completion of pre-treatment procedures. Patients will receive avelumab 10mg/kg as an IV infusion Q2W. In order to mitigate infusion related reactions, a premedication with an antihistamine and with acetaminophen 30 to 60 minutes prior to each dose of avelumab is mandatory (for example, 25-50 mg diphenhydramine and 500- 650 mg acetaminophen IV or oral). The treating oncologist may use equivalent or similar medications as available at their discretion.

Two cycles will be given before starting radiation therapy. After 2 cycles of avelumab, a short course of SBRT (after the end of Cycle 2 and before Cycle 3, Day 1) will be delivered to a portion of MPM that is symptomatic or at risk of causing symptoms. Avelumab treatment continues during and after RT for up to two years or until disease progression. Avelumab may be continued after disease progression at the discretion of the investigator if criteria in section 4.2 are met.

The first day of dosing is considered Day 1 of the cycle. Day 1 of Cycle 1 is considered the date of first dose and is used to determine the maximum 24 months of treatment. Trial treatment should be administered on Day 1 of each cycle. Trial treatment may be administered up to 3 days before or after the scheduled Day 1 of each cycle due to administrative reasons. All trial treatments will be administered on an outpatient basis.

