10.6 Serial Imaging

CT of the chest, abdomen, and pelvis, preferably with contrast, will be performed every 2 months after completing SBRT (+/- 14 days) through the follow-up period.

10.7 End of treatment visits at 30 and 90 days after last avelumab (+/- 14 days)

1. History and physical examination, including height, weight, vital signs (temperature, pulse rate, respiration rate, blood pressure), and performance status (Karnofsky)
2. Report side effects
3. CBC with differential and platelet count, CMP (including Na, Cl, BUN, Creatinine, K, CO2, glucose, AST, ALT, alkaline phosphatase, total bilirubin, calcium, albumin, and total protein)
4. Serum or urine pregnancy test for women of childbearing potential
5. Free T4/TSH

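### PFS ends at removal from study for progression, not at first documented progression, so the event is late or lost for patients kept on avelumab after progression

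*Combined protocol and SAP*

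**What the plan says.** Section 12.0 starts PFS at the first avelumab treatment and runs it "until removal from study due to progressive disease (defined by modified RECIST 1.1) or death". It adds: "Removal from study due to toxicity will be counted as censoring". Section 14.0 says only that PFS and OS will be analyzed by Kaplan-Meier; it gives no event date and no other censoring rule.

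On treatment, Section 9.1.1 states: "Avelumab treatment continues during and after RT for up to two years or until disease progression". Continuation is nevertheless permitted. Section 4.3 says: "Patients may continue Avelumab after RECIST-defined radiologic progression of disease if the following criteria are met", and Section 9.1.1 says: "Avelumab may be continued after disease progression at the discretion of the investigator if criteria in section 4.2 are met". (The criteria are printed under 4.3.)

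Section 13.1, on removal from study, holds two lists. The first gives reasons for permanently stopping avelumab, including intolerable adverse events and, by reference, the reasons in Section 9. The second gives reasons for removal once treatment has ended: death, pregnancy, withdrawal of consent and non-compliance with follow-up.

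Observation continues after treatment. Section 4.4 follows all subjects, with assessments every 2 months, "for up to 1 year following completion of avelumab or disease progression". Under Section 10.6, CT "will be performed every 2 months after completing SBRT (+/- 14 days) through the follow-up period".

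**The concern.** The parenthesis in the PFS definition says how progression is judged, not which date counts. The date that counts is the date of removal. For a patient who stops avelumab at the progressive scan, the two nearly coincide. For a patient treated past progression they do not, and the time between the scan and the eventual stop is added to PFS. If that patient later stops for toxicity, the censoring sentence applies and the progression never enters the analysis. Both routes lengthen reported PFS.

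The terminology adds to the problem. Section 12.0 speaks of removal from study where Section 13.1 is mostly describing the end of avelumab, while Section 4.4 keeps patients under follow-up after progression. Two analysts could extract different dates from the same record.

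PFS is a named secondary endpoint, and Section 3.2 cites PFS for avelumab alone in mesothelioma, so an informal comparison is likely. An event date that depends on when treatment was ended would blur it.

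**Working it through.** **No PFS figure to reproduce.** The plan's only design calculation is the two-stage safety rule in Section 14.0. P(declared safe) = sum over x = 0 to 2 of Bin(x; 13, p) × P(Y ≤ 4 − x), with Y ~ Bin(14, p). This gives 0.809 at p = 0.1 (stated 80%) and 0.047 at p = 0.3 (stated 5%). PFS does not enter, so changing its definition leaves the rule alone.

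**Which event date applies, if removal means stopping avelumab**

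| Patient | Date under Section 12.0 | First documented progression |
|---|---|---|
| Stops at the progressive scan | About the scan date | Scan date |
| Continues, later stops for progression | Date of stopping | Earlier scan date |
| Continues, dies on treatment | Date of death | Earlier scan date |
| Continues, later stops for toxicity | Censored; progression lost | Earlier scan date |

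**Size of the delay (illustration)**

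From the documents: median PFS 17.1 weeks (95% CI 6.1 to 30.1) and 24-week PFS 38.4% on avelumab alone (Section 3.2); response assessment "every 2 months after completing SBRT (approximately 8 weeks, or every 4 cycles") (Section 12.0); at most 27 patients.

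Assumed, because the documents give no value:
- exponential PFS;
- share p of progressing patients treated past progression: 10%, 20%, 30%;
- delay d: 8 or 16 weeks (one or two scan intervals);
- share q of first events that are deaths, hence not delayed: 10% or 20%;
- median survival after progression m: 35 or 15 weeks; a death during the delay ends PFS.

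With L = ln 2 / 17.1 = 0.0405 and mu = ln 2 / m:

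S*(t) = exp(−Lt) + p(1 − q) × ∫ L exp(−Lu) exp(−mu(t − u)) du, for u from max(0, t − d) to t.

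Without delay, S(24) = exp(−0.0405 × 24) = 0.378, close to the cited 38.4%.

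Example: p = 0.3, q = 0.1, d = 16, m = 35, t = 24. The integral from 8 to 24 is 0.291, so S*(24) = 0.378 + 0.3 × 0.9 × 0.291 = 0.457.

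| p | d (weeks) | q = 0.2, m = 15: median / 24-week PFS | q = 0.1, m = 35: median / 24-week PFS |
|---|---|---|---|
| 10% | 8 | 17.7 / 0.388 | 17.9 / 0.390 |
| 10% | 16 | 18.3 / 0.397 | 18.8 / 0.404 |
| 20% | 8 | 18.3 / 0.397 | 18.6 / 0.402 |
| 20% | 16 | 19.4 / 0.416 | 20.3 / 0.430 |
| 30% | 8 | 18.9 / 0.407 | 19.3 / 0.414 |
| 30% | 16 | 20.5 / 0.434 | 21.8 / 0.457 |

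For scale, the 95% half-width around 0.378 in 27 patients is 1.96 × √(0.378 × 0.622 / 27) = 0.183, about 18 points. The largest shift in the table is 0.457 − 0.378 = 0.079, about 8 points. Progressions lost to a later toxicity stop are not modeled.

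**Toxicity censoring (minor and conditional)**

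Suppose 20% of patients are prone to a toxicity stop, placed uniformly over weeks 7 to 16, that is, after SBRT in the study calendar. Kaplan-Meier with censoring at the stop gives 17.1 weeks. The true median is about 17.8 weeks if the later hazard is halved, 17.1 if unchanged and 16.2 if doubled. The bias can go either way or be nil.

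**The case against.** The strongest defense is that Section 12.0 works for most patients. Section 13.1 is headed as removal from study, and its first list covers stopping avelumab for toxicity and, through Section 9, for progression. On that reading the PFS wording has a clear meaning, the default is to stop at progression, and continuation is restricted by the Section 4.3 criteria. The endpoint is descriptive, and the illustrated inputs come from outside the documents. At a 10% to 20% share and an 8-week delay, the median moves by only 0.6 to 1.5 weeks, less than the 14-day imaging window.

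Most of this stands, and it limits the point to patients treated past progression. It does not supply the missing date: the plan separates progression from stopping for these patients and never says that the scan date governs.

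A reader might go further and infer that only death could end PFS, since the second list in Section 13.1 omits progression. The documents do not support that: the list covers removal after treatment has ended, and the reading would make the stated progression event meaningless. Nor can one say that the event is always merely late, because a later toxicity stop would censor it. The toxicity-censoring rule is prespecified, and no direction of bias can be claimed for it.

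**Conclusion.** The point holds for patients treated past progression. Following Section 12.0 as written gives them an event that is too late or missing, and the effect is to lengthen reported PFS. This rests on reading removal as stopping avelumab, the most natural sense of Sections 9.1.1 and 13.1 together.

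The likely effect is small. Across the illustrated range the median is 0.6 to 4.7 weeks too long (17.7 − 17.1 to 21.8 − 17.1), and every median stays inside the cited interval of 6.1 to 30.1 weeks. These sizes depend entirely on the assumed share, delay and death rates. The case for change is that a named endpoint lacks a reproducible event date, not that the distortion is large. No test, comparison or safety decision depends on it.

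The toxicity-censoring part is secondary: it sets aside progression and death that scheduled follow-up would show, with unknown and possibly no bias. The mixed use of removal from study is a wording fault that should be corrected at the same time.

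**What to change.** In Section 12.0, define PFS as the time from first avelumab dose to first documented progression by the stated criteria or death from any cause, whichever comes first, whether or not avelumab continues. Censor event-free patients at their last evaluable tumor assessment.

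In Sections 12.0 and 13.1, use one term for stopping avelumab and another for leaving the study.

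Optionally, report a PFS estimate that counts events seen after a toxicity stop alongside the prespecified toxicity-censored one.

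The cost is a few sentences. Patients who received SBRT need no new scans, because 2-monthly CT is already scheduled through follow-up. No treatment rule changes. Reported PFS may be slightly shorter.

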9.4 Dose Modification and Discontinuation

9.4.1 Adverse Drug Reactions (ADRs) Requiring Avelumab Discontinuation or Dose Modification

Any Grade 4 ADRs require treatment discontinuation with avelumab except for single laboratory values out of normal range that are unlikely related to study treatment as assessed by the investigator, do not have any clinical correlate, and resolve within 7 days with adequate medical management.

Any Grade 3 ADRs require treatment discontinuation with avelumab except for any of the following:

- Transient (\leq 6 hours) Grade 3 flu-like symptoms or fever, which are controlled with medical management
- Transient (\leq 24 hours) Grade 3 fatigue, local reactions, headache, nausea, emesis that resolves to Grade \leq 1
- Single laboratory values out of normal range (excluding Grade \geq 3 liver function test increase) that are unlikely related to study treatment according to the Investigator, do not have any clinical correlate, and resolve to Grade \leq 1 within 7 days with adequate medical management
- Tumor flare phenomenon defined as local pain, irritation, or rash localized at sites of known or suspected tumor

Any Grade 2 ADR should be managed as follows:

- If a Grade 2 ADR resolves to Grade \leq 1 by the last day of the current cycle, treatment may continue.
- If a Grade 2 ADR does not resolve to Grade \leq 1 by the last day of the current cycle, infusions should not be given on the following cycle. If at the end of the following cycle the event has not resolved to Grade 1, the subject should permanently discontinue treatment with avelumab (except for hormone insufficiencies, that can be managed by replacement therapy; for these hormone insufficiencies, up to 2 subsequent doses may be omitted).
- Upon the second occurrence of the same Grade 2 ADR (except for hormone insufficiencies that can be managed by replacement therapy) in the same subject, treatment with avelumab will be permanently discontinued.

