10.8 Followup Period Visits (every 2 months +/- 14 days)

Patients will be seen and evaluated by a physician every 2 months during the follow-up period. They will undergo standard of care serial imaging as per Section 10.5, blood work (CBC, CMP, Free T4/TSH), and a history and physical examination.

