14.0 BIOSTATISTICS

The primary endpoint, the safety of a combination of avelumab and SBRT, will be defined based on the rate of any grade 3 or higher non-hematologic toxicity within the first 3 months after SBRT (for the rest of the section this will be referred to as AE). A two-stage stopping rule will be used to protect patients' safety. If 3 or more among the first 13 patients develop AEs, then the trial will be stopped and declared unsafe. Otherwise, an additional 14 patients will be enrolled and treated. If, among the total 27 patients, 5 or more patients are observed to have AEs, then the trial will also be declared unsafe. This stopping rule has a power of 80% declaring the true AE rate of 0.1 or lower safe, and a type 1 error rate (alpha) of 5% declaring true AE rate of 0.3 or higher safe.

For secondary endpoints, the overall response and the irradiated lesion and non-irradiated lesion response rates (4 months from start date of the combined therapy) based on RECIST 1.1 response criteria will be summarized by sample proportions and their confidence intervals. PFS and OS will be evaluated by Kaplan-Meier method.

For the exploratory objectives, we will evaluate changes of T-cell infiltration and serum immunophenotype at baseline and after SBRT + immunotherapy both in- and outside the irradiated field. The former is measured as numerical values so we will use Wilcoxon signed-rank test. The latter is categorical so we will tabulate it and employ the marginal homogeneity test. Due to the expected small sample size, results will be interpreted cautiously. The imaging studies using DWI-MRI and DCE-MRI, and FDG-PET will be correlated with biopsy results by McNemar's tests.

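### PFS counts removal for toxicity as censoring although CT follow-up continues, so observed progressions and deaths may be left out, with a bias whose direction is unknown

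*Combined protocol and SAP*

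**What the plan says.** Section 12.0 measures PFS from the start of avelumab "until removal from study due to progressive disease (defined by modified RECIST 1.1) or death". The next sentence adds: "Removal from study due to toxicity will be counted as censoring". On analysis, Section 14.0 says only that "PFS and OS will be evaluated by Kaplan-Meier method". It gives no sensitivity analysis, competing-risk analysis or fuller censoring rule for PFS.

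On what happens after toxicity:

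- Section 9.4.1: "Any Grade 3 ADRs require treatment discontinuation with avelumab except for any of the following". The consequence is loss of the drug.
- Section 13.1 has two lists. The first gives reasons to stop avelumab permanently and includes intolerable adverse events. The second gives reasons for removal from the study after treatment ends: death, pregnancy, withdrawn consent and non-compliance with follow-up. Toxicity is not on the second list.
- Section 4.4: "All subjects will be followed for survival and assessed every 2 months", for up to 1 year after avelumab is completed or disease progresses.
- Section 10.6: CT "will be performed every 2 months after completing SBRT (+/- 14 days) through the follow-up period".
- Section 10.8, on follow-up visits: "They will undergo standard of care serial imaging as per Section 10.5". Serial imaging is in fact Section 10.6, and the cross-reference appears to be off by one.

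**The concern.** A patient who stops avelumab for toxicity stays on the CT schedule, so later progression or death would normally be observed. If the Section 12.0 sentence applies to that patient, those events do not count, including a death from the toxicity itself after the stop. Kaplan-Meier then treats the patient as having the same later risk as patients still being followed. The censoring event is closely tied to the trial's primary subject, severe toxicity, and to loss of the study drug, so that assumption cannot be taken for granted.

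The wording also leaves room for two analyses. One analyst could censor at the avelumab stop and another only at departure from follow-up, giving two PFS curves from the same data. The event has a related weakness. It is tied to removal for progression, yet Section 4.3 allows avelumab to continue after RECIST progression under stated conditions, so the removal date and the progression date can differ.

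**Working it through.** **Step 1: what removal from study can mean in Section 12.0.** Two readings are possible.

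- *Leaving follow-up.* Toxicity is not a listed ground for this in Section 13.1. The one explicit toxicity-linked removal is in Section 9.1.2 (SBRT not possible within the 6-week delay allowed for managing toxicity), and those patients are replaced. On this reading the sentence applies to almost nobody.
- *Stopping avelumab.* The same paragraph speaks of removal from study for progression, which is also absent from the post-treatment list in Section 13.1. Removal there appears to mean coming off treatment. This is the more natural reading, but the text does not state it.

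**Step 2: effect on the estimate under the second reading.** The plan gives no target or precision for PFS, so there is no planned figure to reproduce. The inputs are:

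- Median PFS 17.1 weeks, from the avelumab-alone mesothelioma cohort in Section 3.2, used as an illustration.
- Assumed: exponential PFS, toxicity stops at week 8, a share q of patients stopping, and hazard multiplied by h after the stop. Neither q nor h is a figure from the documents.

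λ = ln 2 / 17.1 = 0.04054 per week. Without any stops, 24-week PFS = exp(−24λ) = 37.8%. Section 3.2 reports 38.4% for that cohort, so the exponential shape is adequate for illustration.

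In this model, patients not censored keep hazard λ, so the censored Kaplan-Meier estimate tends to exp(−24λ) = 37.8% whatever q and h are. With all events counted:

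S(24) = (1−q)·exp(−24λ) + q·exp(−8λ − 16hλ)

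The second exponential is 0.523 for h = 0.5, 0.378 for h = 1, 0.198 for h = 2 and 0.103 for h = 3.

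| q | h | All events counted | Censored | Censored minus all events |
|---|---|---|---|---|
| any | 1 | 37.8% | 37.8% | 0 |
| 7.5% | 2 | 0.925×0.378 + 0.075×0.198 = 36.4% | 37.8% | +1.4 points |
| 30% | 2 | 0.70×0.378 + 0.30×0.198 = 32.4% | 37.8% | +5.4 points |
| 30% | 3 | 0.70×0.378 + 0.30×0.103 = 29.6% | 37.8% | +8.2 points |
| 30% | 0.5 | 0.70×0.378 + 0.30×0.523 = 42.1% | 37.8% | −4.3 points |

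For q = 30% and h = 2 the all-events median is 15.2 weeks, against 17.1 censored.

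**Step 3: patients affected.** Those still event-free at the week-8 stop number 27·q·exp(−8λ) = 27·q·0.723. That is 1.5 patients at q = 7.5% and 5.9 at q = 30%, assuming full accrual. Even at h = 1, where there is no bias, about 5.9 × (1 − exp(−16λ)) = 5.9 × 0.477 = 2.8 events by week 24 would be left out in the 30% case.

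**Step 4: sensitivity to the timing of stops.** A simulation of 400,000 patients per scenario, with a constant hazard of stopping set so that q is the probability of a stop by week 24, gives the same pattern (censored versus all events):

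- q = 30%, h = 2: 37.8% versus 33.5%.
- q = 30%, h = 1: 38.0% versus 37.9%.
- q = 30%, h = 0.5: 37.7% versus 41.2%.
- q = 7.5%, h = 2: 37.8% versus 36.8%.

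If toxicity-prone patients instead differ from the start, the directions are unchanged at q = 30%: 33.5% versus 30.9% for h = 2, and 41.4% versus 44.8% for h = 0.5.

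**The case against.** The strongest reply is that Section 12.0 censors removal from study, not the stopping of avelumab. Read literally, a patient who stops the drug but remains on follow-up CT is not removed, is not censored and loses no events. This stands as an ambiguity, so one cannot say that the plan certainly discards observed events. It does not rescue the sentence, which on that reading has almost no use.

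A reader might infer that frequent toxicity stops by themselves push PFS upward. They do not: at hazard ratio 1 there is no bias at any frequency, and below 1 the direction reverses. Nor do the documents show that these patients fare worse. Section 3.1 calls the disease almost universally lethal, but that describes everyone's risk, not the relative risk after a toxicity stop. Section 3.2 notes durable checkpoint-inhibitor activity in other solid tumours even after treatment ends, which leaves the opposite direction open.

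A reader might also take 30% as the design's own stopping share. In Section 14.0 the figure 0.3 is a rate of grade 3 or higher non-hematologic toxicity within 3 months after SBRT, not a discontinuation rate. Sections 9.4.1 and 9.5 contain grade 3 exceptions and routes to resuming avelumab. At a true toxicity rate of 0.3, the first-stage rule would also stop the trial about 80% of the time, so full accrual would be unlikely. The 7.5% is likewise an adverse event rate on avelumab alone.

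Finally, the shifts are small beside sampling error. With 27 patients the 95% half-width around 38% is about 1.96 × √(0.38 × 0.62 / 27) = 18 points. That limits the importance of the point but gives no reason to leave out events that were seen.

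**Conclusion.** The concern holds in a limited form. On the natural reading, the only PFS analysis excludes progressions and deaths after a toxicity stop although the protocol schedules the CTs that would show them. The censoring may be informative, but its direction cannot be settled from the documents. Under the assumptions shown, the 24-week estimate is 1.4 points too high at 7.5% stopping with a doubled hazard and 5.4 to 8.2 points too high at 30% stopping with a doubled or tripled hazard. It is correct at hazard ratio 1, and 4.3 points too low at 30% stopping with a halved hazard. A claim that PFS will look better simply because the regimen is toxic is not supported.

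PFS is a secondary, descriptive endpoint with no hypothesis attached. Neither the two-stage safety decision nor the definition of overall survival is affected. The definition should nevertheless be corrected before analysis.

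**What to change.** Replace the PFS definition and the toxicity-censoring sentence in Section 12.0 with the following: time from first avelumab dose to first documented progression by modified RECIST or death from any cause, whichever comes first, regardless of avelumab discontinuation for toxicity. Censor event-free patients at the last adequate CT. Keep censoring at the toxicity stop only as a labelled sensitivity analysis. Dating the event by documented progression also removes the difficulty with treatment beyond progression. The same rewrite should state how new anticancer therapy begun before progression is handled.

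Reconcile Sections 4.4, 10.6, 12.0 and 13.1 so that removal from study has one meaning, distinct from stopping avelumab.

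The cost is a short rewrite with no new visits or scans. The PFS figure may become slightly less favourable if patients stopped for toxicity do worse than the rest.
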